## 5 Objectives and endpoints

### 5.1 Primary objectives and endpoints Part A

*Primary objective 1:*

To evaluate the safety and tolerability of different doses of CH505TF Env gp120 in HIV-uninfected healthy adults

*Primary endpoint 1:*

Local and systemic reactogenicity signs and symptoms, laboratory measures of safety, and AEs and SAEs

*Primary objective 2:*

To evaluate binding antibody responses elicited by different doses of the CH505TF gp120 vaccine

*Primary endpoint 2:*

HIV-specific binding Ab responses as assessed by binding Ab multiplex assay 2 weeks after the third vaccination with CH505TF gp120

### 5.2 Secondary objectives and endpoints Part A

*Secondary objective 1:*

To evaluate the ability of different doses of the vaccine regimen to elicit memory B cells that differentially bind CH505 wildtype gp120 TF Env vs the mutant CH505 Env IΔ371 gp120

*Secondary endpoints 1:*

Differential binding to CH505 gp120 compared to CH505 IΔ371 protein as assessed by flow cytometry analysis of the frequency of the differential binding memory B cells 2 weeks after the third vaccination with CH505TF gp120

*Secondary objective 2:*

To evaluate the ability of different doses of the vaccine regimen to elicit HIV-specific nAbs

*Secondary endpoints 2:*

- Magnitude and breadth of neutralizing antibody responses against autologous viral isolates as assessed by area under the magnitude-breadth curves 2 weeks after the third vaccination with CH505TF gp120 and at additional timepoints of interest following vaccination

- Magnitude and breadth of neutralizing antibody responses against a cross-clade panel of isolates induced 2 weeks after the third vaccination with CH505TF and at additional timepoints of interest following vaccination

*Secondary objective 3:*

To evaluate HIV-specific T-cell responses induced by different doses of the CH505TF vaccine

*Secondary endpoint 3:*

Response rate and magnitude of CD4+ T-cell responses as assessed by intracellular cytokine staining assays (ICS) 2 weeks after the third vaccination with CH505TF and at additional timepoints of interest following vaccination

*Secondary objective 4:*

To isolate single B cells with desired specificities and determine lineage characteristics

*Secondary endpoint 4:*

Monoclonal antibodies may be evaluated for binding and neutralization including tier 2 virus bnAb activity and CD4 binding site loop binding, neutralization of autologous TF or mutant CH505 viruses

### **5.3 Exploratory objectives Part A**

*Exploratory objective 1:*

Based on the primary and secondary analyses, to further evaluate the immunogenicity of the different doses of CH505TF gp120 at additional timepoints of interest.

*Exploratory objective 2:*

To assess vaccine-induced follicular helper T cell (Tfh) responses

### **5.4 Primary objectives and endpoints Part B**

*Primary objective 1:*

To evaluate the safety and tolerability of EnvSeq-1 vaccines administered with or without DNA Mosaic-Tre *env* in HIV-uninfected healthy adults

*Primary endpoint 1:*

Local and systemic reactogenicity signs and symptoms, laboratory measures of safety, and AEs and SAEs

*Primary objective 2:*

To evaluate and compare vaccine-induced humoral responses elicited by EnvSeq-1 vaccines administered in sequential and additive protein immunizations, with and without DNA

*Primary endpoints 2:*

- Magnitude and breadth of neutralizing antibody response against autologous viral isolates 2 weeks after the fourth and sixth (final) vaccinations with and without DNA
- Magnitude and breadth of neutralizing antibody responses against a panel of heterologous isolates induced 2 weeks after the fourth and sixth (final) vaccinations with and without DNA

## **5.5 Secondary objectives and endpoints Part B**

*Secondary objective 1:*

To evaluate and compare HIV-1 specific binding Ab responses elicited by EnvSeq-1 vaccine administered in sequential and additive protein immunization, with and without DNA

*Secondary endpoints 1:*

- HIV-specific binding Ab responses as assessed by binding Ab multiplex assay 2 weeks after the fourth and sixth (final) vaccinations with and without DNA
- Differential binding to EnvSeq-1 gp120 compared to CH505 IΔ371 protein

*Secondary objective 2:*

To evaluate HIV-specific T-cell responses induced by different doses of the EnvSeq-1 vaccines

*Secondary endpoint 2:*

Response rate and magnitude of CD4+ T-cell responses as assessed by ICS assays 2 weeks after the fourth and sixth (final) vaccinations with EnvSeq-1 vaccines with and without DNA

*Secondary objective 3:*

To isolate single B cells with desired specificities and determine lineage characteristics

*Secondary endpoint 3:*

Monoclonal antibodies may be evaluated for binding and neutralization including tier 2 virus bnAb activity and CD4 binding site loop binding, neutralization of autologous TF or mutant CH505 viruses, and differential binding to CH505 gp120 compared to CH505 IΔ371 protein.

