**Table 3-1 Schema**

Study arm	N	Month 0 (Day 0)	Month 2 (Day 56)	Month 4 (Day 112)	Month 8 (Day 224)	Month 12 (Day 364)
Part A						
Group 1	12	20 mcg CH505TF	20 mcg CH505TF	20 mcg CH505TF	20 mcg CH505TF	20 mcg CH505TF
Group 2	12	100 mcg CH505TF	100 mcg CH505TF	100 mcg CH505TF	100 mcg CH505TF	100 mcg CH505TF
Group 3	12	400 mcg CH505TF	400 mcg CH505TF	400 mcg CH505TF	400 mcg CH505TF	400 mcg CH505TF
Group 4	6	placebo	placebo	placebo	Placebo	placebo
Total Part A		42 (36/6)				
Study arm	N	Month 0 (Day 0)	Month 2 (Day 56)	Month 4 (Day 112)	Month 8 (Day 224)	Month 12 (Day 364)
Part B						
Group 5	20	TBD mcg CH505TF + placebo	TBD mcg CH505w53 + placebo	TBD mcg CH505w78 + placebo	TBD mcg CH505w100 + placebo	TBD mcg CH505w100 + placebo
Group 6	20	TBD mcg CH505TF + 4 mg DNA Mosaic-Tre	TBD mcg CH505w53 + 4 mg DNA Mosaic-Tre	TBD mcg CH505w78 + 4 mg DNA Mosaic-Tre	TBD mcg CH505w100 + 4 mg DNA Mosaic-Tre	TBD mcg CH505w100 + 4 mg DNA Mosaic-Tre
Group 7	20	TBD mcg CH505TF + placebo	TBD mcg CH505TF, w53 + placebo	TBD mcg CH505TF, w53, w78 + placebo	TBD mcg CH505w53, w78, w100 + placebo	TBD mcg CH505w78, w100 + placebo
Group 8	20	TBD mcg CH505TF + 4 mg DNA Mosaic-Tre	TBD mcg CH505TF, w53 + 4 mg DNA Mosaic-Tre	TBD mcg CH505TF, w53, w78 + 4 mg DNA Mosaic-Tre	TBD mcg CH505w53, w78, w100 + 4 mg DNA Mosaic-Tre	TBD mcg CH505w78, w100 + 4 mg DNA Mosaic-Tre
Group 9	10	placebo + placebo	placebo + placebo	placebo + placebo	placebo + placebo	placebo + placebo
Total Part B		90 (80/10)				
Total Part A + Part B		132 (116/16)				

Safety data and immune responses after Month 4 in Part A will inform the protein dose for Part B.

GLA-SE will be admixed with all proteins. The total dose of GLA-SE will be 10 mcg at all timepoints. The total volume for protein plus adjuvant for injection is 1 mL, mixed 1:1 by volume.

If the dose of each protein in Groups 5 and 6 is 20 mcg, the total dose of each protein in Groups 7 and 8 will also be 20 mcg. If the dose of each protein in Groups 5 and 6 is 100 mcg or 400 mcg, the dose of each protein in Groups 7 and 8 will be 100 mcg.

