#### **4.1.3 Rationale for DNA Mosaic-Tre env as a universal helper immunogen**

[figure not shown]
It is known that considerable T-cell help is required for the amount of affinity maturation needed to drive bnAbs and that those individuals chronically infected with HIV who spontaneously make bnAbs have higher levels of blood CD4 T cells that are phenotypically similar to T follicular helper T cells (Tfh) [25]. Previous work in non-human primates suggested that including a DNA vaccine with the protein can increase the quantity and quality of the induced antibody response compared to immunization with protein alone [26,27]. Furthermore co-administration of DNA and protein in the same limb elicited higher systemic binding and neutralizing antibodies compared to DNA alone or DNA prime followed by an antibody boost [26]. Pavlakis and colleagues illustrated the potential immunologic advantages of co-administration of protein with DNA in non-human primate studies whereby the animals that received DNA vaccine (either alone or co-administered with a protein) had higher levels of vaccine-induced T-cell responses. Moreover, the group that received DNA concurrently with protein had higher binding Ab responses than DNA or protein alone [28,29]. Pissani, et al. also showed in rabbits that DNA and protein co-administration increased the magnitude, avidity, and neutralizing potency compared to administration of protein alone. In addition, their study indicated that antibody responses using a mismatched DNA and protein elicited comparable or higher responses compared to matched vaccines [27]. These data support inclusion of a DNA vaccine in the regimen to assess and compare binding antibody responses and differential binding induced by immunization with and without the DNA. We hypothesize that the combined administration of DNA and protein will elicit stronger humoral and cellular responses than the protein alone.

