## 5.6 Exploratory objectives Part B

*Exploratory objective 1:*

To further evaluate the immunogenicity of the vaccine regimens at different timepoints

*Exploratory objective 2:*

To determine the B cell repertoire of HIV-specific B cells

*Exploratory objective 3:*

To assess vaccine-induced follicular helper T cell (Tfh) responses

*Exploratory objective 4:*

To correlate vaccine-induced B-cell and Tfh responses to EnvSeq-1 gp120s with responses to the gut microbiome using optionally-provided stool specimens

*Exploratory objective 5:*

To compare immune responses in groups 6 and 8 with DNA to groups 5 and 7 without DNA

*Exploratory objective 6:*

To further evaluate immunogenicity of each vaccine regimen, additional immunogenicity assays may be performed, including on samples from other timepoints, based on the HVTN Laboratory Assay Algorithm.

*Exploratory objective 7:*

To conduct analyses related to furthering the understanding of HIV, immunology, vaccines, and clinical trial conduct.

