To test for differences among the vaccine arms in Part A and separately in Part B, first a Kruskal-Wallis rank test or an F-test (depending on the normality assumption) will be used to test for overall differences. Secondly, if the overall test is significant at the 2-sided 0.05 level, then individual tests comparing the 2 adjacent pairs of vaccine arms (Part A) and all 6 pairs of 4 vaccine arms (Part B) will be done unless pre-specified. If rank-based tests are used then the tests will be inverted to construct Hodges-Lehmann point estimates and 2-sided  $(1-0.05/k) \times 100\%$  CIs about the differences in location centers of the  $k = 2$  (Part A) or  $k = 6$  (Part B) pair-wise comparisons of vaccine arms. If actual-value tests are used then the Dunnett's procedure will be used to construct simultaneous confidence intervals about the pairs of mean differences for the many-to-one comparisons [62] when multiple vaccine arms are each compared with 1 common control arm. When all pair-wise comparisons between the multiple vaccine arms are of interest, the Tukey procedure [63] will be used. If only specific comparisons between pairs of the multiple vaccine arms are of interest, the Holm-Bonferroni procedure will be used. An appropriate data transformation (eg,  $\log_{10}$  transformation) may be applied to better satisfy assumptions of symmetry and homoscedasticity (constant variance). Significance of the differences between pairs will be evaluated using 2 procedures, first based on whether the simultaneous 95% CIs exclude zero and secondly based on whether the nominal (unadjusted) 95% CIs exclude zero.

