### 6.4.4.4 Analysis of CD4+ T-cell response as measured by the ICS assay

The analysis of CD4+ T-cell response rates as measured by the ICS assay will be evaluated and compared as described under the general approach. For each T-cell subset, the positivity call for each peptide pool will include a multiple comparison adjustment for the number of peptide pools used in the assay. In general, the Mixture Models for Single-cell Assays (MIMOSA) statistical framework [72] and/or the Fisher's exact test-based positivity criteria will be used. Details of the positivity criteria will be discussed in the SAP. The magnitude of marginal response will be analyzed as described for quantitative data in the general approach section. For each T-cell subset, graphs will be used to display the background-subtracted magnitudes for each participant by protein, treatment arm and timepoint. When 3 or more cytokines are being measured by the ICS assay, the polyfunctionality of ICS responses may also be analyzed as an exploratory endpoint. Besides descriptive plots of the magnitude of polyfunctional responses, the COMPASS (Combinatorial Polyfunctionality analysis of Antigen-Specific T-cell Subsets) statistical framework may also be used to perform joint modelling of multiple T-cell subsets of different cytokine combinations. For example, the functionality score (FS) and the polyfunctionality score (PFS) may be used to summarize the multi-parameter ICS responses.

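### Part B's T-cell objective asks about dose, which Part B does not randomize, and no pooled DNA contrast is named for CD4+ ICS magnitude in the secondary analysis

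*Combined protocol and SAP*

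**What the plan says.** Section 5.5, secondary objective 2 for Part B, reads "To evaluate HIV-specific T-cell responses induced by different doses of the EnvSeq-1 vaccines". Its endpoint is CD4+ ICS response rate and magnitude "2 weeks after the fourth and sixth (final) vaccinations with EnvSeq-1 vaccines with and without DNA". Part A has the same sentence with the other product name, "To evaluate HIV-specific T-cell responses induced by different doses of the CH505TF vaccine" (Section 5.2).

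Under Table 3-1, "Safety data and immune responses after Month 4 in Part A will inform the protein dose for Part B". Groups 5 to 8 then differ by sequential or additive protein and by DNA or its placebo.

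Section 4.1.3 states the expected DNA effect: "We hypothesize that the combined administration of DNA and protein will elicit stronger humoral and cellular responses than the protein alone". Exploratory objective 5 (Section 5.6) is "To compare immune responses in groups 6 and 8 with DNA to groups 5 and 7 without DNA".

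On analysis, Section 6.4.4.4 sends ICS response rates to the general approach, where Section 6.4.4.1 tests any two arms and pooled groups at two-sided p ≤ 0.05. On magnitude it says "The magnitude of marginal response will be analyzed as described for quantitative data in the general approach section". The quantitative part of Section 6.4.4.1 gives an overall test at 0.05 and, if that is significant, "all 6 pairs of 4 vaccine arms (Part B) will be done unless pre-specified". Pairs are judged twice, by simultaneous and by unadjusted 95% intervals.

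Section 6.1.2 defines two pooled Part B contrasts at 5% each (Groups 5+6 vs 7+8, and 5+7 vs 6+8). It lists binding antibody, memory B cells and neutralization for them, not ICS.

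**The concern.** An objective should name a factor that the design varies. Part B's primary objective 2 and secondary objective 1 both name schedule and DNA. This one names dose, for which no randomized contrast exists, and so does not match its own endpoint.

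The consequence is practical. DNA is in the regimen to supply CD4 T-cell help (Section 4.1.2), and CD4+ ICS is the assay that bears on it most directly. Because the objective names dose, no primary or secondary objective names the DNA comparison for T cells. For magnitude, the secondary analysis goes to an overall four-arm test and six pairs, although the 2×2 layout allows a stronger pooled test that the protocol has already defined for other endpoints.

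**Working it through.** **Can any Part B contrast isolate dose?** Table 3-1 and Section 4.5.1 give the rule. If 20 or 100 mcg is selected, the per-protein dose is the same in Groups 5 to 8. If 400 mcg is selected, Groups 5 and 6 receive 400 mcg and Groups 7 and 8 receive 100 mcg of each protein. The dose difference then coincides exactly with sequential versus additive. Total protein per visit also differs whenever the additive arms combine two or three proteins, but that too follows schedule. No pair or pool of arms differs by dose alone.

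**Inputs for power** (Section 6.1.2, binding antibody): 94% non-zero; non-zero log10 response Normal with mean 4.06 and SD 0.391; 10% missing, so 0.9 × 20 = 18 evaluable per arm and 0.9 × 40 = 36 per pooled group; two-sided rank sum tests; 0.05 per pooled contrast and 0.05/6 = 0.0083 per pair. The documents give no mean, SD, zero rate or expected DNA effect for ICS, so using these inputs for ICS is an assumption.

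**The plan's own figures, by simulation.**
- Pooled, 0.80 SD (0.80 × 0.391 = 0.313 log10): 80.5–81.3%, stated 80%.
- Pooled, 0.90 SD: 88.4–89.9%, stated 90%.
- Pairwise at 5%/6, 1.81 SD: 90.4–90.9%, stated 90%.
- Pairwise at 5%/6, 1.63 SD (1.63 × 0.391 = 0.637 log10): 84–85%, stated 80%, so slightly conservative.

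By the plan's own 80% figures, the effect needed in a pair is 1.63/0.80 = 2.04 times that needed in the pooled contrast.

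**The stated route for ICS magnitude.** Each simulated trial has four arms of 18. Both DNA arms are shifted by d × 0.391, with no schedule effect. A DNA pair (5 vs 6, or 7 vs 8) counts only if the Kruskal-Wallis test has p ≤ 0.05 and the pair's rank sum test is significant. The pair is tested at 0.05/6 for the simultaneous intervals and at 0.05 for the unadjusted ones. Ranges show separate runs.

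| DNA effect, zeros | Pooled 6+8 vs 5+7 at 5% | Given pair, 5%/6 | At least one pair, 5%/6 | Given pair, unadjusted | At least one pair, unadjusted |
|---|---|---|---|---|---|
| 0.80 SD, 6% | about 81% | 22–24% | 39–42% | 43–44% | 62–63% |
| 0.90 SD, 6% | about 89% | 30–32% | 52% | 54–55% | 73–74% |
| 0.80 SD, none | 90–91% | 32–33% | 53–54% | 56–57% | 75% |
| 0.80 SD, 30% (assumed) | 35% | 5% | 10% | 12% | 21% |

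The overall test alone has 64% power in the first row, which caps everything that follows it. Absolute power depends heavily on the zero rate. The ordering does not change in any row.

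**The case against.** Several points on the other side stand.

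- A reader might infer that the whole DNA T-cell question is left to weak pairwise tests. The documents do not support that. Pooled groups are planned for ICS response rates, half of this endpoint, at p ≤ 0.05. Exploratory objective 5 makes the pooled DNA comparison for immune responses with no assay excluded. The gap is confined to magnitude as a secondary analysis.
- A reader might infer that half the data are discarded. They are not: each pair uses two arms, but the two DNA pairs together, and the overall test, use all four.
- A reader might infer that nothing under this objective can be evaluated. The verb is to evaluate, without compare, and the endpoint shows what will be measured. What cannot be answered is the dose question.
- Quoting only the 5%/6 results would understate the plan, because Section 6.4.4.1 also reads pairs from unadjusted intervals. Those figures are shown alongside.
- 0.80 SD is the effect at which the plan sizes the pooled binding-antibody test, so pooled power near 80% holds by construction. Only the comparison between routes is informative.
- Section 6.4.4.1 leaves room for prespecified comparisons, and for Holm-Bonferroni when only certain pairs matter. Nothing in the document uses that room to name a pooled contrast for ICS magnitude.

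**Conclusion.** The point holds in limited form. The objective's wording does not fit Part B's arms or its own endpoint and reads as carried over from Part A. For CD4+ ICS magnitude, the secondary analysis names a weaker route than the pooled contrast the protocol already defines.

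At 0.80 SD the difference is about 81% against 22–24% for a given DNA pair at 5%/6, or about 44% unadjusted. For at least one of the two pairs it is 39–42%, or about 63% unadjusted. These figures rest on binding-antibody inputs, an equal DNA effect under both schedules, no schedule effect, and the rank-based branch of Section 6.4.4.1. They do not show that the trial is underpowered for T cells, because the documents give nothing from which to judge that. This is a matter of wording and prespecification for a secondary endpoint in a phase 1 trial; no change of dose or design is implied.

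**What to change.** 1. Section 5.5: restate secondary objective 2 so that it evaluates and compares T-cell responses between the sequential and additive EnvSeq-1 regimens, each with and without DNA, in parallel with secondary objective 1.
2. Section 6.4.4.4: for CD4+ ICS magnitude, name the two pooled contrasts of Section 6.1.2 (Groups 6+8 vs 5+7, and 7+8 vs 5+6) at 5% each, and keep the six pairs as supportive.
3. Section 6.4.4.1: the pooled groups for response rates are referred to Section 4.1.2, which is the study rationale and defines none. Point the reference to Section 6.1.2.

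The cost is a few sentences, made before any unblinded ICS analysis. There are two drawbacks. Two more secondary contrasts are named, unadjusted across secondary endpoints as Section 6.4 already states. The pooled contrast also averages over schedule: if DNA gave 0.80 SD under one schedule and nothing under the other, the average shift would be (0.80 + 0)/2 = 0.40 SD. The supportive pairs should therefore be reported beside it.

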## 5.6 Exploratory objectives Part B

*Exploratory objective 1:*

To further evaluate the immunogenicity of the vaccine regimens at different timepoints

*Exploratory objective 2:*

To determine the B cell repertoire of HIV-specific B cells

*Exploratory objective 3:*

To assess vaccine-induced follicular helper T cell (Tfh) responses

*Exploratory objective 4:*

To correlate vaccine-induced B-cell and Tfh responses to EnvSeq-1 gp120s with responses to the gut microbiome using optionally-provided stool specimens

*Exploratory objective 5:*

To compare immune responses in groups 6 and 8 with DNA to groups 5 and 7 without DNA

*Exploratory objective 6:*

To further evaluate immunogenicity of each vaccine regimen, additional immunogenicity assays may be performed, including on samples from other timepoints, based on the HVTN Laboratory Assay Algorithm.

*Exploratory objective 7:*

To conduct analyses related to furthering the understanding of HIV, immunology, vaccines, and clinical trial conduct.

## 6 Statistical considerations

### 6.1 Accrual and sample size calculations

Recruitment into Part A will target 42, and recruitment into Part B will target 90, healthy, HIV-uninfected adults aged 18 to 50 years old at low risk of HIV infection in regions where clade B is the predominant clade. Since enrollment is concurrent with receiving the first study vaccination, all participants will provide some safety data. However, for immunogenicity analyses, it is possible that data may be missing for various reasons, such as participants terminating from the study early, problems in shipping specimens, low cell viability of processed peripheral blood mononuclear cells (PBMCs) or high background. Immunogenicity data from 17 phase 1 and 2 phase 2a HVTN vaccine trials, which began enrolling after June 2005 (data as of September 2014), indicate that 10% is a reasonable estimate for the rate of missing data. For this reason, the sample size calculations in Section 6.1.2 account for 10% of enrolled participants having missing data for the primary immunogenicity endpoint.

#### 6.1.1 Sample size calculations for safety

The ability of the study to identify SAEs can be expressed by the true event rate above which at least 1 event would likely be observed and the true event rate below which no events would likely be observed. Specifically, in each vaccine arm of Part A of the study ( $n = 12$ ), there is a 90% chance of observing at least 1 event if the true rate of such an event is 17.5% or more; and there is a 90% chance of observing no events if the true rate is 0.8% or less. In all vaccine arms of the Part A of the study combined ( $n = 36$ ), there is a 90% chance of observing at least 1 event if the true rate of such an event is 6.2% or more; and there is a 90% chance of observing no events if the true rate is 0.2% or less. In each vaccine arm of Part B of the study ( $n = 20$ ), there is a 90% chance of observing at least 1 event if the true rate of such an event is 10.9% or more; and there is a 90% chance of observing no events if the true rate is 0.5% or less. In all vaccine arms of the Part B of the study combined ( $n = 80$ ), there is a 90% chance of observing at least 1 event if the true rate of such an event is 2.9% or more; and there is a 90% chance of observing no events if the true rate is 0.1% or less.

Probabilities of observing 0, 1 or more, and 2 or more events among arms of size 12 and 20 are presented in Table 6-1 for a range of possible true adverse event rates. These calculations provide a more complete picture of the sensitivity of this study design to identify potential safety problems with the vaccine.

**Table 6-1 Probability of observing 0 events, 1 or more events, and 2 or more events, among arms of size 12 and 20, for different true event rates**

True event rate (%)	Pr(0/12)	Pr(1+/12)	Pr(2+/12)	Pr(0/20)	Pr(1+/20)	Pr(2+/20)
1	88.6	11.4	0.6	88.8	18.2	1.7
4	61.3	38.7	8.1	44.2	55.8	19.2
10	28.2	71.8	34.1	12.2	87.8	60.8
20	6.9	93.1	72.5	1.2	98.8	93.1
30	1.4	98.6	91.5	0.1	99.1	<0.1
40	0.2	99.8	98.0	<0.1	>99.9	<0.1

An alternative way of describing the statistical properties of the study design is in terms of the 95% confidence interval for the true rate of an adverse event based on the observed data. Table 6-2 shows the 2-sided 95% confidence intervals for the probability of an event based on a particular observed rate. Calculations are done using the score test method [59]. If none of the 36 participants receiving a vaccine regimen in Part A experience a safety event, the 95% 2-sided upper confidence bound for the true rate of such events in the total vaccinated population is 9.6%. For each individual Part A vaccine arm ( $n = 12$ ), the 2-sided upper confidence bound for this rate is 24.2%. If none of the 80 participants receiving a vaccine regimen in Part B experience a safety event, the 95% 2-sided upper confidence bound for the true rate of such events in the total vaccinated population is 4.6%. For each individual Part B vaccine arm ( $n = 20$ ), the 2-sided upper confidence bound for this rate is 16.1%.

**Table 6-2 Two-sided 95% confidence intervals based on observing a particular rate of safety endpoints for arms of size 12 and 20**

Observed event rate	95% Confidence interval (%)
0/12	[0, 24.2]
1/12	[1.5, 35.4]
2/12	[4.7, 44.8]
0/36	[0, 9.6]
1/36	[0.5, 14.2]
2/36	[1.5, 18.1]
0/20	[0, 16.1]
1/20	[0.9, 23.6]
2/20	[2.8, 30.1]
0/80	[0, 4.6]
1/80	[0.2, 6.7]
2/80	[0.7, 8.7]

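### Table 6-1 misprints five of the 18 cells for arms of 20, including <0.1% where the probability exceeds 99%, so it misstates the safety sensitivity of a Part B arm

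*Combined protocol and SAP*

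**What the plan says.** Section 6.1.1 describes safety sensitivity in two ways. The prose gives, for each arm size, the true event rate at which at least one event is 90% likely and the rate at which no event is 90% likely. For a Part B arm of 20 these are 10.9% and 0.5%. Table 6-1 then adds detail: "Probabilities of observing 0, 1 or more, and 2 or more events among arms of size 12 and 20 are presented in Table 6-1" for true rates from 1% to 40%. The protocol introduces the table's purpose with the words "These calculations provide a more complete picture of the sensitivity of this study design to identify potential safety problems with the vaccine."

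Each row gives the true rate (%), then Pr(0), Pr(1+) and Pr(2+) for n = 12, then the same three for n = 20. Three of the four affected rows read:

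- 1% row: "1 88.6 11.4 0.6 88.8 18.2 1.7"
- 4% row: "4 61.3 38.7 8.1 44.2 55.8 19.2"
- 30% row: "30 1.4 98.6 91.5 0.1 99.1 <0.1"

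The fourth is the 40% row, whose n = 20 entries are <0.1, >99.9 and <0.1.

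**The concern.** Three faults show without any calculation.

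- **1% row.** Pr(0/20) and Pr(1+/20) are complements, but 88.8 + 18.2 = 107.0. The 88.8 also exceeds the 88.6 printed for an arm of 12, although a larger arm cannot be more likely to show no event at the same rate.
- **30% row.** 0.1 + 99.1 = 99.2, not 100.
- **Pr(2+/20) column.** It runs 1.7, 19.2, 60.8, 93.1, <0.1, <0.1. This probability can only rise with the event rate. It also cannot be lower than the value for an arm of 12, which is 91.5 at 30% and 98.0 at 40%.

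Safety and tolerability is primary objective 1 of Part B (Section 5.4), and Table 6-1 is the only place where the plan states the chance of two or more events in a Part B arm. Read literally, it says that an arm of 20 would almost never show two events of a kind that affects 30% to 40% of recipients, when it almost always would. It also overstates by 7 points the chance that a 1% event goes unseen. That entry is the easiest to accept at face value, because it looks plausible beside 88.6.

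**Working it through.** **Inputs, all from Section 6.1.1.** Arm sizes n = 12 (Part A) and n = 20 (Part B); true rates p = 1, 4, 10, 20, 30 and 40%. Dropout does not enter, because every enrolled participant receives the first vaccination and gives some safety data.

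**Formulas (exact binomial)**

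- Pr(0) = (1 − p)^n
- Pr(1+) = 1 − (1 − p)^n
- Pr(2+) = 1 − (1 − p)^n − n·p·(1 − p)^(n−1)

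**Check of the method.** All 18 cells for n = 12 reproduce to the printed decimal. For example, at 30% the results are 1.38, 98.62 and 91.50, against 1.4, 98.6 and 91.5 printed. The method is therefore the one the plan used.

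**All cells for n = 20** (printed → exact, %; wrong cells in bold)

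| True rate | Pr(0/20) | Pr(1+/20) | Pr(2+/20) |
|---|---|---|---|
| 1% | **88.8 → 81.79** | 18.2 → 18.21 | 1.7 → 1.69 |
| 4% | 44.2 → 44.20 | 55.8 → 55.80 | **19.2 → 18.97** |
| 10% | 12.2 → 12.16 | 87.8 → 87.84 | 60.8 → 60.83 |
| 20% | 1.2 → 1.15 | 98.8 → 98.85 | 93.1 → 93.08 |
| 30% | 0.1 → 0.08 | **99.1 → 99.92** | **<0.1 → 99.24** |
| 40% | <0.1 → 0.004 | >99.9 → 99.996 | **<0.1 → 99.95** |

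Thirteen cells agree with the printed values and five do not.

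**The five cells written out**

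- 1%, Pr(0): 0.99^20 = 0.8179
- 4%, Pr(2+): 1 − 0.96^20 − 20(0.04)(0.96^19) = 1 − 0.4420 − 0.3683 = 0.1897
- 30%, Pr(1+): 1 − 0.7^20 = 1 − 0.0008 = 0.9992
- 30%, Pr(2+): 1 − 0.0008 − 20(0.3)(0.7^19) = 1 − 0.0008 − 0.0068 = 0.9924
- 40%, Pr(2+): 1 − 0.6^20 − 20(0.4)(0.6^19) = 1 − 0.00004 − 0.00049 = 0.9995

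**Neighbouring Part B figures.** For n = 20, 1 − 0.1^(1/20) = 10.87% and 1 − 0.9^(1/20) = 0.525%, which match the stated 10.9% and 0.5%. For n = 80 the same formulas give 2.84% and 0.13%, stated as 2.9% and 0.1%. The score interval for 0/20 has an upper bound of 16.11%, against 16.1% in Table 6-2, and the other Table 6-2 intervals also reproduce.

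**The case against.** The arithmetic is not open to dispute; the argument is about importance.

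- **The main sensitivity statements are right.** The prose thresholds for a Part B arm and its Table 6-2 intervals are correct, as are 13 of the 18 n = 20 cells. This stands: the error is confined to Table 6-1. However, neither the prose nor Table 6-2 gives Pr(2+), so they do not supply the wrong entries in that column.
- **No decision uses these cells.** Arm sizes are not derived from them. Table 11-1 triggers pauses and reviews by individual graded events, AE comparisons between arms are descriptive (Section 6.4.3.2), and the move to Part B rests on review of Part A safety data (Section 11.3.2). This stands.
- **The worst errors are conspicuous and give no false reassurance about detecting harm.** Few careful readers would believe <0.1 directly below 93.1, and those two cells understate sensitivity. This is fair for those cells. It is weaker for 88.8, which is exposed only by adding it to its neighbour or by comparing it with the smaller arm.
- **Two of the five errors are trivial.** The 0.2-point and 0.8-point errors do not affect interpretation. They are still wrong at a precision that every other cell meets.
- **Single characters may have been misread when the PDF was converted to text.** This cannot be excluded for 88.8 or 99.1, but it does not readily explain <0.1 in place of 99.2. The rest of the table is intact, and five separate faults confined to the n = 20 columns would be needed. The sponsor can settle it against the source table.

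**Conclusion.** The point holds. Exactly five n = 20 cells of Table 6-1 are wrong, by +7.0, +0.2, −0.8, about −99 and about −99.9 percentage points. The first and the last two are material. The conclusion rests only on the stated arm sizes and on independent events with a common rate, the binomial model that reproduces the other 31 of the table's 36 cells.

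What is wrong is the sensitivity printed in this table for an arm of 20. The design's true sensitivity is unaffected, and for frequent events it is far better than the table says. It should be corrected because these are stated detection probabilities for a primary objective, but it does not call the design into question.

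**What to change.** In the n = 20 columns of Table 6-1, replace:

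- 1% row, Pr(0/20): 88.8 with 81.8
- 4% row, Pr(2+/20): 19.2 with 19.0
- 30% row, Pr(1+/20): 99.1 with 99.9
- 30% row, Pr(2+/20): <0.1 with 99.2
- 40% row, Pr(2+/20): <0.1 with 99.9

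The last value is 99.948 before rounding, so 99.9 is right at one decimal. Check the entries against the source table at the same time. This is a text correction only, with no change to sample size, analysis or conduct.
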